**Exclusion criteria:**

- Patient on chronic anticoagulation
- Pregnant women
- Non-english speaking patients
- Any individuals who are unable to give informed consent
- Any individual with diminished capacity to give informed consent
- Allergy to local anesthetics
- Patients who remain intubated overnight after surgery or who are unable to provide information regarding their pain immediately postoperatively
- Daily use of opioid for more than three weeks
- Significant liver disease, defined as liver enzymes greater than 3x the upper limit of normal
- Lack of patient cooperation including those patients who refuse a MAC anesthetic
- Patient with pectoral muscle involvement of tumor
- Contraindication to regional anesthesia
  - Infection at injection site
  - Inability to guarantee sterile equipment or sterile conditions for the block
  - Patient refusal
  - Severe Coagulopathy or bleeding disorder

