**Randomization procedure:**

Patients will be identified by members of the treatment team in either the surgeon's clinic, pre-assessment clinic, or preoperative area. Patients who have opted out of research will not be asked to participate in the study. Patients will be approached to consent for the study by a surgeon, anesthesiologist, or member of the research team. Patients who agree to participate in the study will sign both a study consent and HIPAA authorization allowing the use of specified information contained in medical records for research purposes.

A random number generator will be used to determine if the patient will have pectoralis liposomal bupivacaine infiltration or bupivacaine infiltration directly into the incision space. The primary or co-investigator will access the number generator in the pre-op area. The website [www.random.org](http://www.random.org) will be used as the random number generator.

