For the surgeon infiltration, the patient will be brought directly to the operating room where intraoperative anesthetic with an opioid-sparing MAC technique will be provided as described below. Just prior to the skin incision, 0.25% bupivacaine will be used to infiltrate the dermis and subcutaneous space in the proposed incision. Throughout the procedure, additional incisional bupivacaine infiltration into the surrounding tissues will be performed as needed for local anesthesia. A total of up to 30 mL of 0.25% bupivacaine will be divided equally for the two sides of the incision. An additional 5 mL of 0.25% bupivacaine will be infiltrated into the pectoralis major muscle at the deep margin of resection. Accidental intravascular injection is minimized by continuous needle movement and frequent aspiration.

The following vital signs will be monitored throughout the procedure: Heart rate, blood pressure, oxygen saturation, and respirations, and patient's state of consciousness. We will monitor the patient until they are brought to the operating room for surgery.

All patients will receive multimodal analgesia in the preoperative area. They will receive 975 mg of oral acetaminophen and 300 mg of gabapentin orally prior to surgery. The intraoperative anesthetic will be an opioid-sparing MAC anesthetic. If patients are unable to tolerate procedure under MAC they would be converted to a general anesthetic with an laryngeal mask airway (LMA). For those patients receiving a lumpectomy with axillary dissection, they will receive a general anesthetic with LMA. Patients will receive IV midazolam 0-2 mg followed by 40-100mg of IV lidocaine, and followed by a propofol infusion and a 0.25 mg/kg bolus of ketamine followed by 0.25 mg/kg /hour infusion of ketamine. Opioids will be avoided unless HR or BP increases by 20 % above baseline. Then only short acting opioids (fentanyl) will be given.

In the recovery room if the patient experiences pain greater than 5/10 they will receive either IV or oral pain medications. If pain score is less than 5 patients will get non opioid medications unless the patient desires an opioid medication.

When the operation is complete the patient will either be brought to the PACU or Phase II. Each day a member of the research team will contact and evaluate the patient for signs of complications and ask the patient their minimum and maximum pain score

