### **Enrollment procedures:**

Patients will be recruited from the group of adult surgical patients at the University of Minnesota undergoing partial mastectomy procedures. Patients will be approached in either the surgeon's clinic or pre-assessment clinic by a research staff member to determine their interest in participation. Subjects interested in the study will be presented with consent and Health and Insurance Portability and Accountability Act (HIPAA) forms, with the REDCap e-consent process being preferentially used. The patient will review the forms with the surgeon, anesthesiologist or other study staff. Subjects will be reminded that participation is completely voluntary, and that they may stop participation at any time without question or penalty. The surgeon or anesthesiologist will answer any questions that the subjects may have about the study. If the patient decides to participate, they will be asked to sign the consent and HIPAA forms. One copy will be saved for study records, and the subject will be provided with a copy of the forms for their own records. If they need additional time to consider enrollment, they will be asked if we can reach out to them by phone the night before surgery or if we should revisit the study with them on the day of surgery. If the patient is unable to be consented prior to day of surgery, the research staff will approach them in the preoperative surgical area. These patients will have significant time to review the study with research staff as well as the physicians performing the procedure due to the fact they arrive several hours prior to their scheduled surgery. All subjects will have enough time to ask questions about the study and the potential risks involved regardless of which venue they are consented. Any patient that refuses to participate in the study at any time point will be placed on a secured list to avoid duplicate attempts to recruit them. All forms will be locked and stored in a file cabinet in the research department. Enrolling consecutive patients will help reduce selection bias. Any patient who does not complete all necessary paperwork and answer questions at the appropriate time intervals will be eliminated from the study. Patients lost to follow-up, or patients who decide not to participate in the study after initial enrollment, or patients who are eliminated from the study for any reason will have their study records shredded and will not be included in the final data-analysis.

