### **Assessments:**

Post-operatively patients will be evaluated 1 and 2 hr post-operatively by the PACU nurse and 6 hrs post-operatively by a medical student or research coordinator. This person will not be aware of the patient's mode of analgesia. The medical student or research coordinator will evaluate at, 24, 48, and 72 hours post injection +/- 5 hours. If sent home they will be contacted via preferred contact method at, 24, 48, and 72 hours post-operatively. Patients will be asked to rate their pain on scale of 0-10. The amount of opioids used by the patient will be recorded as will any other adjuvant pain medication used. Any modality related complications will be recorded. The patients will be asked at 72 hours post-injection to fill out a quality of recovery and OBAS survey. All complications will be recorded from time of consent to last follow up date. Patients will be called at 3, 6, and 12 months post operatively to fill out a chronic pain survey.

All data will be recorded in a locked encrypted database. Data collection will continue until Postoperative day ( POD ) #3. Should patients be re-admitted to the hospital in the next two weeks (Up to POD #19) for pain a notation will be made in study records. Additional contacts by the research assistant or medical student will continue up until the 3, 6, and 12 month postoperative times.

An analysis of the total cost of analgesics (including patient costs for opioid prescriptions) will be tabulated at the conclusion of the study to determine the most cost effective treatment option as this will be added into the cost of hospitalization including the number of days each patient spent in the hospital.

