### **Stopping Criteria:**

This study will be stopped if 5% of the subjects experience local toxicity. If  $\geq 10\%$  of the subjects develop an infection at the injection site, the protocol will be discontinued. Additionally, if any patient experiences a serious adverse event as a result of the study medications as determined by the principle investigator, they will be discontinued from the study.

Local anesthetic toxicity is defined as patients who experience local anesthetic toxicity symptoms such as new onset of tinnitus, metallic taste in mouth, numbness around lips, seizures, heart block or new arrhythmia after injection of local anesthetic for up to monitoring period of 5 days.

**Notification:** When a study participant, voluntarily or involuntarily, is eliminated from the study protocol, the Principal Investigator and Associate Investigators will be notified.

**Adverse reactions:** Adverse or unexpected occurrences resulting from the treatment utilized in the protocol will be reported to the Principal Investigator and the Associate Investigators. These individuals will discuss these reactions or untoward events and implement changes in the protocol accordingly. Investigators will meet regularly to discuss problems encountered with the study protocol.

**Modifications to protocol:** Alterations that may become necessary in the protocol during the study period will be made by agreement of the investigators. Patients will be notified of any relevant protocol changes.

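### Patients removed after a related serious adverse event or a post-treatment exclusion have no secured follow-up or place in the analysis, and their place in the stopping tallies is not stated

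*Combined protocol and SAP*

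**What the plan says.** All sections are in the combined protocol and SAP.

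- **Stopping Criteria** sets a toxicity limit ("This study will be stopped if 5% of the subjects experience local toxicity") and a 10% limit for infection at the injection site. It then adds a rule for the individual patient: if anyone has "a serious adverse event as a result of the study medications as determined by the principle investigator, they will be discontinued from the study". The removal is from the study, not only from treatment.
- **Exclusion criteria** lists "Patients who remain intubated overnight after surgery or who are unable to provide information regarding their pain immediately postoperatively".
- **Randomization procedure** places allocation before surgery: "The primary or co-investigator will access the number generator in the pre-op area".
- **Enrollment procedures** has two removal rules. One is for incomplete data: "Any patient who does not complete all necessary paperwork and answer questions at the appropriate time intervals will be eliminated from the study". The other covers patients lost, withdrawn or "eliminated from the study for any reason will have their study records shredded and will not be included in the final data-analysis".
- **Assessments** says "All complications will be recorded from time of consent to last follow up date".
- **Data Safety Monitoring** sends all serious adverse events to a safety board. **Definition of a Serious Adverse Event** requires a report to the IRB within 5 days.

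**The concern.** Both rules remove patients because of something that happens after treatment, and one of them removes patients because of harm. A reported event is not the same as a followed event. If contact ends on removal, the course and resolution of the worst events go unrecorded, and so do the 72-hour and the 3-, 6- and 12-month assessments. If the patient is also left out of the analysis, the comparison between arms no longer covers everyone randomized, and the safety profile can look cleaner than what was seen.

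The judgement that triggers removal is not blinded. The principal investigator decides relatedness and, under Subjects, is among those who place the Pec blocks. Blinding is described only for those who assess outcomes. Removal could therefore differ between arms.

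**Working it through.** The plan gives stopping limits as percentages, not counts, so it has no figure of its own to reproduce here. The planned 112 patients (Statistical Considerations) serve only as a denominator.

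1. **What discontinuation can achieve.** Under Treatment technique, the block is finished before the patient enters the operating room, and the surgeon's infiltration ends with the operation. Once a related serious event is recognised, usually little or no study drug is left to withhold. Leaving the study then mainly ends follow-up.

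2. **When the exclusion acts.** Allocation is in the pre-op area and treatment comes before or during surgery. Overnight intubation and inability to report pain are known only later, so this is a post-randomization exclusion. The planned anesthetic is MAC; patients who cannot tolerate it are managed as "they would be converted to a general anesthetic with an laryngeal mask airway (LMA"), and those having axillary dissection receive an LMA from the start. Overnight intubation would thus be unplanned, though not necessarily caused by the study drug.

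3. **What follows removal.** No section describes contact after removal. Complications are recorded up to the last follow-up date, and early removal can be read as bringing that date forward, possibly inside the 5-day toxicity window. If a discontinued patient counts as eliminated, the records are destroyed and the patient is not analysed. The plan does not equate the two terms, but its elimination wording is broad.

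4. **The stopping tallies, as an illustration.** Assume that each limit is met at or above its percentage, that the denominator is all 112, and that removed cases leave both numerator and denominator.
   - Toxicity: 0.05 × 112 = 5.6, so 6 cases are needed; 6/112 = 5.4%. With one case dropped, 5/111 = 4.5%, and the limit is not met.
   - Infection: 0.10 × 112 = 11.2, so 12 cases are needed; 12/112 = 10.7%. With one dropped, 11/111 = 9.9%, not met.
   - Earlier in the trial, with 40 treated: 2/40 = 5.0% meets the toxicity limit; 1/39 = 2.6% does not.

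   The smallest true count x with (x − k)/(112 − k) ≥ 0.05, when k toxicity cases are dropped:

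   | Dropped (k) | True cases needed (x) | Tally seen | True share |
   |---|---|---|---|
   | 0 | 6 | 6/112 = 5.4% | 5.4% |
   | 1 | 7 | 6/111 = 5.4% | 7/112 = 6.3% |
   | 2 | 8 | 6/110 = 5.5% | 8/112 = 7.1% |
   | 3 | 9 | 6/109 = 5.5% | 9/112 = 8.0% |

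5. **Chance of meeting the 5% limit in one look at 112.** Let X be binomial(112, p) and let each case be dropped with probability s; both p and s are assumptions. For p = 10%, the chance is 97%, 85% and 49% at s = 0, 25% and 50%. For p = 8%, it is 89%, 67% and 29%.

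**The case against.** The strongest reply is that serious events have more reporting routes than any others. They go to the board, which gives a written determination of severity and recommended actions, and to the IRB. Risks and the precautions paragraph also require complications to be noted, charted and reported. This stands: a reader might infer that such events vanish, and the documents do not support that. What these routes secure is the report, not the later follow-up or the place in the analysis.

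A reader might also infer that removed patients leave the stopping count. The plan does not say so. The toxicity limit counts subjects who experience the event, which comes before any removal. The limits count toxicity and injection-site infection, not serious events as such. Milder toxicity symptoms such as tinnitus or a metallic taste would seldom trigger the serious-event rule, whereas seizure, heart block or new arrhythmia could fall under both. The 6-to-5 reversal also needs exactly six cases: with seven and one dropped, 6/111 = 5.4% still meets the limit. All that can be said is that the plan does not state that these patients stay in the numerator and denominator, and that destroying records would make the tally hard to verify.

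Finally, a reader might take the exclusion as removing patients for drug harm. That is not shown. Inability to report pain could reflect sedation from the planned anesthetic, and overnight intubation could have other causes. It remains an exclusion after randomization, whatever its cause.

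**Conclusion.** The concern holds for follow-up and analysis. The plan removes patients with a related serious adverse event from the study, excludes others on events after treatment, and provides no follow-up for either group. Exclusion from the final analysis and loss of records follow if *discontinued* or *excluded* means *eliminated*, which the plan leaves open.

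For the stopping rules, the finding is a gap: the denominator is undefined and the status of removed patients is unstated. The change from 5.4% to 4.5% shows how much one patient could matter if removal applied to the tally; it is not a prediction. The number of patients affected cannot be estimated from the documents. The point should be settled by amendment, because destroyed records cannot be recovered at analysis.

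**What to change.** Amend four sections so that they agree. None of the changes touches dosing or clinical care.

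- **Stopping Criteria:** state that a patient with a related serious adverse event remains in the study, is followed until the event resolves or stabilises and through the planned 72-hour and 3-, 6- and 12-month contacts, and counts in every stopping tally. Define the denominator of both limits as all treated patients.
- **Exclusion criteria:** delete the item on overnight intubation and inability to report pain. Record the affected pain scores as not obtainable, with the reason. Opioids given in hospital can still be taken from the medication administration record.
- **Enrollment procedures:** exempt these patients from elimination, record destruction and omission from the analysis. Without this, a patient whose pain score is unobtainable could still be eliminated for incomplete answers, and the other edits would fail.
- **Assessments:** make clear that removal or a serious event does not bring forward the last follow-up date for recording complications.

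The cost is a few sentences in one amendment, a few extra contacts and some missing early pain scores.

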## **Background and Significance:**

Liposomal bupivacaine is a multivesicular formulation of bupivacaine that has been shown to provide up to 72 hours of analgesia compared to bupivacaine, which provides up to 24 hours of analgesia post injection. These two medications have been compared in incisional infiltration but have yet to be compared in the setting of a pectoralis (“Pec”) infiltration vs incisional infiltration. A Pec 1 infiltration is an injection of local anesthetic in between the pectoralis major and pectoralis minor muscle layers. A Pec 2 infiltration is an injection of local anesthetic between the pectoralis minor and serratus anterior muscle layers or deep to the serratus anterior. These layers are found using an ultrasound, which is a beam of high frequency sound that allows one to visualize images in the body. With the ultrasound it is possible to visualize the needle as it pierces the fascial covering of the pec minor or serratus anterior layer and watch as the local anesthetic is injected into this plane. This is done on both sides of the chest wall to provide analgesia to the skin, muscle, and facial layers of the chest wall if the procedure is bilateral or just on one side if unilateral. Data has shown the Pec infiltration to provide useful pain control after breast surgery, however it is of limited duration provided by bupivacaine.

Incisional infiltration. The surgeon will infiltrate local anesthetic (bupivacaine) into the surgical site at the start of the procedure, within the subcutaneous and dermal regions immediately surrounding the incision. Additional incisional bupivacaine infiltration will be performed as needed throughout the procedure. Accidental intravascular injection is minimized by continuous needle movement and frequent aspiration.

This will be the first study of its kind looking prospectively at Pectoralis 1 and 2 blocks with liposomal bupivacaine compared to surgeon infiltration for postoperative pain in breast partial mastectomy procedures.

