**Treatment technique:**

For the Pec infiltration, the patient will be in the supine position. The pectoralis major and pectoralis minor muscle layers will be identified via ultrasound. Using sterile technique, a nerve block needle will be inserted and advanced under ultrasound guidance until it is below the fascial covering of the pec minor muscle layer. Gentle aspiration for air or blood will be performed in 5cc incremental doses. Then injection of 10 mL of bupivacaine 0.25% with epinephrine 1:200,000 and 10mL of a mixture of liposomal bupivacaine and saline (5 mL liposomal bupivacaine and 5 mL saline) for a total injection for pec 1 block of 20 mL. For each 5cc of local anesthetic injected, aspiration will be performed. Upon completion of the injection the needle will be removed. We will then use the ultrasound probe to identify the second rib on anterolateral chest wall and

move the probe to the 4th rib. Here we will identify the pec minor and serratus anterior muscles. We will advance our needle under ultrasound-guidance beneath pec minor and above serratus anterior or if unable to visualize the serratus/pec minor border will inject under the serratus anterior. Here we will inject 10 mL 0.25% bupivacaine with epinephrine 1:200,000 followed by 20 mL mixture of 15 mL liposomal bupivacaine and 5 mL saline for a total volume of 30mL for Pec 2 Block. Upon completion of the injection, the needle will then be removed and the patient will be monitored in the preoperative area until he/she is brought into the operating room for their procedure.

If deemed necessary for coverage the surgeon will be allowed to inject additional local anesthetic up to a maximum of 40 mL of 0.25% bupivacaine. This will be noted in the chart.

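### The toxicity and infection events in the stopping criteria are not ascertained alike in the two arms, so the counts do not cleanly reflect block harm and cannot fairly be compared between groups

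*Combined protocol and SAP*

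**What the plan says.** Under Stopping Criteria, the toxicity rule reads "This study will be stopped if 5% of the subjects experience local toxicity". Toxicity is described by symptoms such as "new onset of tinnitus, metallic taste in mouth, numbness around lips, seizures, heart block or new arrhythmia after injection of local anesthetic", over a window of up to 5 days. The infection rule applies when 10% or more "of the subjects develop an infection at the injection site, the protocol will be discontinued". Both rules use all subjects as the denominator. Neither is split by arm, neither says which local anesthetic injection is meant, and the term injection site is not defined.

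Under Treatment technique, the Pec block is given before surgery, and afterwards "the patient will be monitored in the preoperative area until he/she is brought into the operating room". Controls go straight to the operating room, where the MAC anesthetic is provided. There, "Just prior to the skin incision, 0.25% bupivacaine will be used to infiltrate the dermis and subcutaneous space in the proposed incision", with more infiltration during the procedure as needed. Patients having axillary dissection receive general anesthesia with an LMA. The sedation sequence is not limited to one arm: "Patients will receive IV midazolam 0-2 mg followed by 40-100mg of IV lidocaine", then propofol and ketamine. The surgeon may also inject bupivacaine in Pec patients where coverage requires it.

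Background and Significance places the control infiltration "within the subcutaneous and dermal regions immediately surrounding the incision". Risks lists wound infection as an item of its own. Data collection says that the groups will be compared regularly for safety and efficacy. A separate section on the relationship of adverse events to study drug has the investigator judge relatedness case by case, but the stopping criteria do not refer to it.

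**The concern.** A safety count can be compared between arms only if the same event has the same chance of being seen and counted in each. Here two features work against that.

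For toxicity, tinnitus, metallic taste and lip numbness exist in the data only if a patient reports them. At the moment of injection a Pec patient can do so, while a control patient under MAC or an LMA general anesthetic mostly cannot.

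For infection, the event is tied to where the needle went. In controls that is the surgical wound. In a Pec patient with no surgeon injection it is the block puncture, and nothing says whether that patient's wound infection counts.

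The first feature tends to raise the reported early symptoms in the Pec arm relative to control. The second tends to raise infections in the control arm. A safety table built from these counts would mix the treatments' effects with differences of setting and labelling. The pooled stopping counts inherit the same mixture.

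**Working it through.** **Toxicity, arms side by side**

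| | Pec arm | Control arm |
|---|---|---|
| Place of injection | Preoperative area | Operating room |
| State at injection | No sedation mentioned for the block (inferred awake) | MAC provided; general anesthesia with LMA if axillary dissection |
| Tinnitus, taste, lip numbness at injection | Can be reported | Largely masked |
| Seizure, heart block, arrhythmia | Observable | Observable |

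The definition runs "after injection of local anesthetic for up to monitoring period of 5 days", so symptoms that persist or arise after emergence can be counted in either arm. This repairs the imbalance only in part. Symptoms that resolve under sedation are lost. Scheduled early contacts end at 72 hours. The plan has modality-related complications recorded but specifies no toxicity-symptom questions.

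**Infection, arms side by side.** In controls the injected tissue is the incision, so a wound infection is an injection-site infection. In Pec patients the site is the puncture, plus the wound if the surgeon also injects. Classification therefore varies between arms, and within the Pec arm according to surgeon injection.

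**Triggers.** Inputs from the plan: 112 patients, 56 per arm, shares of 5% and 10%.
- Toxicity: 0.05 × 112 = 5.6, so 6 events.
- Infection: 0.10 × 112 = 11.2, so 12 events.
- If all events fell in the Pec arm, these are 6/56 = 10.7% and 12/56 = 21.4%.

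**Chance of reaching a trigger.** The pooled count is X + Y, with X ~ Bin(56, Pec rate) and Y ~ Bin(56, control rate), independent. P(X + Y ≥ trigger) is exact and is evaluated once at full enrolment, because the plan gives no schedule for applying the rules. The documents state no event rates, so every rate below is an assumption.

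Toxicity, trigger 6:

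| Counted rate, Pec | Counted rate, control | Meaning | P(trigger) |
|---|---|---|---|
| 5% | 5% | full detection | 0.49 |
| 5% | 2.5% | half of control events masked | 0.24 |
| 5% | 0% | no counted control events | 0.06 |
| 10% | 0% | no counted control events | 0.49 |
| 15% | 0% | no counted control events | 0.86 |

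The first two rows show the effect of masking. The last three show that the pooled count still rises with block harm.

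Background symptoms in both arms, with no toxicity from the study injection: 1% gives 0.001, 2% gives 0.025, 3% gives 0.12, 5% gives 0.49.

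Infection, trigger 12:
- Assumed wound-infection rate of 5% in both arms: expected counted events are 0.05 × 56 = 2.8 in controls, and from 0 (no surgeon injection) to 2.8 (all injected) in the Pec arm if wounds count only where injected.
- No counted Pec infections: control rates of 5%, 10%, 15% and 20% give P(trigger) below 0.001, 0.008, 0.13 and 0.45.
- Pec puncture rate 10%: control rates of 5%, 10% and 15% give 0.13, 0.45 and 0.76.

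So the control wound-infection rate moves the infection rule materially only when it is high or when puncture infections are also frequent.

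**The case against.** A reader might infer that the counts cannot reflect the block's harm at all. The documents do not support that. Seizures, heart block and arrhythmia can be seen under sedation, vital signs are monitored during the procedure, the symptom list is illustrative, and the calculations show the pooled rule responding to Pec toxicity.

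A reader might also infer that IV lidocaine biases the comparison, since the definition does not exclude it. It goes to both arms, so it adds background, not an arm difference. The sedation that follows it would also mute the patient-reported symptoms it caused. What differs is its order: after the block in Pec patients, before infiltration in controls. That is a reason to record onset times, and it is not evidence of bias.

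Nor is it right that the plan has no attribution step. The investigator relatedness assessment exists, and serious events go to a safety board. The gap is that the toxicity rule does not refer to that assessment.

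Three further objections carry weight. The stopping rules are pooled and compare no arms, and the planned between-group comparison does not name these two counts. Pec patients are later sedated and may be injected by the surgeon, so neither contrast is clean and the net size of the toxicity bias is unknown. The infection asymmetry by itself hardly threatens the 12-event trigger at a 5% wound rate.

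What stands is that reportability at injection differs by arm, that the injection site is a different place in each arm, and that a general between-group safety comparison is planned on data collected this way.

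**Conclusion.** The concern holds in limited form. As written, the toxicity and infection events are ascertained differently in the two arms, so their counts are not comparable between groups and only imperfectly reflect harm from the block. The pooled rules remain informative, and nothing here shows that their thresholds are wrong.

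For the toxicity rule, masking half of control events halves the chance of reaching the trigger, from 0.49 to 0.24, under assumed 5% true rates. For the infection rule, the asymmetry alone is negligible at an assumed 5% wound rate. Its effect is on the comparison, where 2.8 expected control events could face as few as none in the Pec arm with identical wound-infection rates.

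The conclusion rests on two readings: that controls are sedated when infiltrated, a strong inference from the order of events under Treatment technique; and that Pec patients are awake for the block, inferred only from the absence of any mention of sedation. If Pec patients were sedated for the block, the toxicity contrast would shrink, but the infection-site contrast would remain.

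**What to change.** 1. Ask the same short toxicity-symptom checklist in both arms at the existing 1, 2, 6, 24, 48 and 72 hour contacts, and base any between-arm toxicity comparison on those common times. Record symptoms reported before surgery after the block separately, and keep counting them for safety monitoring.
2. Record surgical-wound infection in both arms under one definition. Report block-puncture infection separately, with block recipients as the denominator. State in Stopping Criteria which of these the infection rule counts.
3. Have the toxicity rule refer to the existing relatedness assessment, and record symptom onset relative to both the study injection and the IV lidocaine.

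The cost is some rewording of Stopping Criteria and a few checklist items, which lengthen existing contacts slightly. No dose, threshold or visit changes. The checklist cannot recover symptoms that came and went under sedation. It makes the later counts comparable and keeps the preoperative reports from being read as an arm difference.
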